2 LIST OF ABBREVIATIONS

3D	3 Dimensional
5-FU	5 fluoro-uracil
AE	Adverse events
ANC	Absolute Neutrophil Count
AP/PA	Anterior to Posterior, Posterior to Anterior
APC	Argon Plasma Coagulation
BED	Biologically Equivalent Dose
BID	Twice Daily
CBC	Complete Blood Count
CBCT	Cone Beam Computed Tomography
CDDP	Cisplatin
Chemo	Chemotherapy
CPC	Cancer Protocol Committee
CRT	Chemoradiotherapy
CT	Computed Tomography
CTCAE	Common Terminology Criteria for Adverse Events
CTEP	Cancer Therapy Evaluation Program
CTV	Clinical Tumor Volume
D10cc	Minimum dose to the 10 milliliters of any volume receiving the highest dose
D2cc	Minimum dose to the 2 milliliters of any volume receiving the highest dose
DCI	Duke Cancer Institute
DCIS	Ductal Carcinoma in situ
DLT	Dose Limiting Toxicity
Dmax	Maximum dose to any voxel within a volume
DUHS	Duke University Health System
DWI	Diffusion weighted imaging
ECOG	Eastern Cooperative Oncology Group
EFRT	Extended Field Radiotherapy
EQD2	Equivalent dose at 2 Gray per fraction
FIGO	International Federation of Gynecology and Obstetrics
G3 or G4	Grade 3 or Grade 4 toxicity
GCP	Good Clinical Practice
GOG	Gynecologic Oncology Group
GTV	Gross Tumor Volume
GU	Genitourinary
GY	Gray
HDR	High Dose Rate
ICRU	International Commission on Radiation Units and Measurement
ID	Identification
IMRT	Intensity Modulated Radiation Therapy (including Volumetric Modulated Arc Therapy)
IRB	Institutional Review Board
KPS	Karnofsky Performance Scale
LDR	Low Dose Rate
LINAC	Linear Accelerator
LRC	Loco-regional control
MRI	Magnetic Resonance Imaging.
MTD	Maximum Tolerated Dose
MV	Megavoltage
NCI	National Cancer Institute

NRG	National Surgical Adjuvant Breast and Bowel Project (NSABP), the Radiation Therapy Oncology Group (RTOG), and the Gynecologic Oncology Group (GOG)
OBI	On board-imaging
OS	Overall Survival
PA	Para-aortic
PET	Positron Emission Tomography
PI	Primary Investigator
PTV	Planning Target Volume
SAE	Serious adverse event
SOC	Safety Oversight Committee
TD5/5	Toxic dose of 5% at 5 years
V18	Partial volume receiving greater than or equal to 18 Gray
WAI	Whole abdominal irradiation
WPRT	Whole Pelvic Radiotherapy

3 PROTOCOL SYNOPSIS

3.1 Purpose

This protocol seeks to utilize a novel method of tumor bed boost delivery and to better understand breast cancer radiation response through the analysis of pre-and post-radiation samples.

Primary Objective:

1. Determine physician and patient-reported rates of good/excellent cosmesis at baseline and 6 months, 1, 2, and 3 years post-treatment as measured by the NRG cosmesis scale.

Secondary Objective:

1. Evaluate changes in circulating free DNA pre and post-radiation in order to identify potential blood based radiation response biomarkers.
2. Assess patient-reported Quality of Life (FACT-B) and patient satisfaction at the same time points as above (primary objective).
3. Assess local control in the treated breast relative to historical controls.
4. To review treatment plans, evaluate delivery techniques, and assess positioning verification images.

Hypotheses

We hypothesize that the boost can be delivered preoperatively to the intact breast tumor with acceptable cosmetic outcomes. Furthermore, we anticipate that pre- and post-radiation blood samples will provide an avenue for understanding breast cancer radiation response.

3.2 Background and Significance

In 1990, the National Institutes of Health concluded that breast conservation, conservative surgery followed by radiotherapy, was the preferred treatment for women with early stage breast cancer as no survival advantage was seen in women receiving a more radical and disfiguring mastectomy. As a result, breast conservation consisting of lumpectomy followed by 6 weeks of daily external beam radiotherapy became the standard of care in the United States (US). Treatment typically consisted of 4.5-5 weeks of whole breast treatment followed by a 1-1.5 week boost to the surgical resection cavity. Unfortunately, some women electing to receive breast conserving surgery struggled to complete the recommended radiotherapy. Patterns of care studies demonstrated that older women, and those living in low-income regions or far from radiotherapy centers, often omitted radiotherapy altogether¹⁻³. Numerous studies have demonstrated that the local recurrence rates in these women receiving conservative surgery alone are unacceptably high^{4,5}.

As a result, there has been much interest in development of a more convenient alternative to standard radiotherapy. Recently, robust data has documented that a 3 week course of whole breast radiotherapy is an efficacious and safe alternative^{6,7} to standard therapy. Much additional work has been done on partial breast irradiation, rapid treatment of the tumor bed plus a small margin of normal tissue, delivered in 1 to 5 days. Randomized data for this approach is beginning to be reported. Preliminary data suggest comparable rates of local control. However, early results are mixed in regards to normal tissue toxicity^{8,9} and may be technique dependent. Finally, numerous investigators have explored the concept of concurrent or intra-operative tumor bed boost, thus eliminating the final 1 to 1.5 weeks of treatment.

3.3 Rationale

A. Rationale for tumor bed boost

Radiotherapy significantly decreases the rate of local recurrence in women receiving conservative surgery¹⁰⁻¹³. A boost to the surgical resection cavity provides a small additional local control benefit at the cost of increased fibrosis and an extra 1 to 1.5 weeks of treatment. Two randomized trials have established the benefit of a tumor bed boost with a consistent relative risk reduction which extends across all subgroups^{14,15}. However, higher risk women clearly derive a much larger absolute benefit from the boost. NCCN guidelines recommend boost treatment in women deemed to be at higher risk of locoregional recurrence. Many radiation

oncologists routinely deliver a boost to all subjects undergoing breast-conserving therapy. In this proposal, women judged as deriving a benefit from a tumor bed boost by the treating investigator based on clinical stage will be eligible for inclusion.

B. Rationale for alternative boost delivery

Radiation has historically involved 6 weeks of daily therapy at a radiation oncology facility. For many women, particularly those who are older, poor, or live in rural areas, this presents a significant hardship. Surveillance, Epidemiology, and End Results (SEER) registry data has noted in the past that many women were not receiving appropriate breast conservation therapy¹⁻³. Inadequate breast conserving therapy (i.e., no radiotherapy, no axillary node evaluation or neither) increased from 10% of women in 1989 to 19% in 1995 attributable in approximately equal amounts to omission of axillary nodal evaluation and radiotherapy. As a result, numerous investigators spent the following decade proposing techniques to shorten the course of radiation.

Two such techniques were the delivery of a concurrent boost and the delivery of the boost at the time of surgical resection. These techniques were evolving simultaneously with partial breast irradiation, but captured a much larger population of women for whom partial breast treatment was not felt to be appropriate. There are now numerous early-phase trials^{16,17} demonstrating favorable outcomes with the concurrent boost technique. In fact, this approach is currently the subject of a recently completed NRG phase III trial. Women felt to be at higher risk of locoregional recurrence were enrolled and randomized to receive a standard course of 4-6 weeks of radiation or a shortened 3 week course of treatment with a concurrent boost.

Intra-operative boost is another technique that has been investigated by a number of groups¹⁸⁻²¹. Doses of 9 to 12 Gy have been utilized in a single fraction. In general, this approach has been well-tolerated with no clear indications of increased toxicity. The key limitation for this technique is the costly intra-operative linear accelerator which is not widely available to many oncologists or subjects.

C. Rationale for single-fraction preoperative technique

We propose in this trial to build on the favorable results of the intraoperative boost trials but using a preoperative delivery approach. We have demonstrated the feasibility of the preoperative approach²² and successfully completed a Phase I dose-finding partial breast trial. The preoperative approach has several advantages: 1) expensive intra-operative equipment is unnecessary, 2) a small intact breast tumor results in significantly less uninvolved breast tissue receiving high radiation doses which likely decreases toxicity; 3) more accurate targeting of the high-risk areas of subclinical disease surrounding the tumor is possible, 4) smaller treatment volumes are amenable to dose escalation which can further accelerate treatment and improve accessibility for subjects, and 5) the pre-operative approach provides a novel opportunity to study breast cancer radiation response.

While delivery of intra-operative treatment is likely to remain limited in its availability, nearly all radiation oncology facilities have the capability of delivering focused external beam radiotherapy. Significant technological advances have been made in recent years that support sophisticated treatment delivery and the ability to modulate the dose as needed to minimize toxicity.

D. Rationale for magnetic resonance imaging (MRI) treatment planning

Target delineation has always been highly subjective in the post-lumpectomy setting. The tumor bed is currently defined as the area of architectural distortion plus surgical clips. Defining this area is subject to inherent variability depending on the bias of the treating physician. Pre-operative assessment of the tumor should certainly improve delineation of the target and the surrounding area at risk. However, the typical tools used for defining breast tumors, mammography and ultrasound, cannot currently be used in conjunction with radiation planning software. MRI, on the other hand, has a growing role in breast imaging and can be used for radiation treatment planning.

E. Rationale for endpoints

Numerous investigators have documented limited toxicity in studies evaluating an intraoperative boost. In addition, we noted no acute dose-limiting toxicities in our Phase I trial delivering preoperative doses greater than the one planned in this study. Therefore, we feel that there is conceptual support from the existing literature for this approach.

Radiotherapy to the intact tumor is a relatively rare event in breast cancer irradiation, particularly in the setting of early stage breast cancer. Tumor and normal tissue radiation response remain relatively poorly understood. Markers capable of predicting radiation response are rare indeed.

3.4 Selection of Subjects and Sample Size

Women judged by clinical stage as someone to whom a tumor bed boost would be offered during conventional radiation therapy will be eligible. As a general guideline, this typically includes women with invasive cancer that are eligible for and electing breast-conserving therapy under the age of 60. Selected women greater than 60 may also be offered a boost at the discretion of the treating investigator. For example, known nodal involvement may prompt a boost in this scenario. Women with in situ cancers <50 are also typically offered a boost though again, certain women greater than 60 may also be included at the discretion of the treating physician.

The final sample size is 40 subjects. Given the broad eligibility criteria and the more than 400 new subjects with invasive breast cancer seen in Radiation Oncology at Duke each year, accrual is anticipated to be complete in 3 years once the first patient is enrolled.

4 SUBJECT ELIGIBILITY

4.1 Inclusion Criteria

1. Women with a biopsy proven diagnosis of ductal carcinoma in situ or invasive carcinoma of the breast. Biopsy tissue (either slides or block) from outside institutions will be reviewed to confirm diagnosis.
2. Breast preservation candidates (no prior breast or nodal radiotherapy, no imaging evidence of multicentric disease preventing resection through a single incision, no pregnant women, and no comorbid conditions precluding surgery)
3. cTis-T3 cancer judged to benefit (by treating radiation oncologist) from a tumor bed boost
4. Women of child-bearing potential must consent to use adequate contraception during the course of the study: (1) surgical sterilization (such as a tubal ligation or hysterectomy), (3) barrier methods (such as a condom or diaphragm) used with a spermicide, or (4) an intrauterine device (IUD). Contraceptive measures such as Plan B (TM), sold for emergency use after unprotected sex, are not acceptable methods for routine use.
5. WBC > 3000, Hgb > 10, platelets >100000 within 30 days of consent
6. Eligible for contrasted MRI on initial evaluation with GFR ≥ 60 ml/min. A diagnostic MRI ordered within 60 days of diagnosis will be considered an acceptable alternative and will not be repeated.
7. Outside breast imaging will be reviewed at Duke to confirm that findings are consistent with trial eligibility

4.2 Exclusion Criteria

1. Breast implant in the breast to be treated (contralateral breast implant is acceptable)
2. Medical conditions that may increase risk for poor cosmetic outcome (i.e. Lupus, rheumatoid arthritis, scleroderma)
3. Subjects unable to receive study treatment planning secondary to body habitus or inability to lie flat on the stomach for at least 1 hour
4. Positive serum pregnancy test
5. Insufficient breast imaging to judge clinical stage
6. Subjects without placement of a biopsy clip at the diagnostic procedure who are unwilling to undergo clip placement.
7. Subjects in whom treatment planning constraints cannot be met

4.3 Inclusion of Women and Minorities

Only women will be eligible for this study. Minority groups will also be eligible and accrual is expected to reflect the population of subjects seen in the Duke Multi-disciplinary Breast Cancer Clinic.

5 TREATMENT PLAN

5.1 Surgery

Surgical tumor resection will be completed 2-4 days after RT delivery (though up to 7 days will be allowed for logistical constraints without considering this a protocol deviation). Subjects will undergo intraoperative lymphatic mapping and sentinel lymphadenectomy as is standard at our institution. Standard axillary nodal dissection is acceptable if there is a contraindication to the sentinel node procedure or if felt to be clinically indicated based on nodal involvement. Negative margins, defined as no tumor on ink, are the institutional standard. Standard pathologic assessment will follow.

5.2 Radiotherapy

Target Volume:

Prior to treatment, a biopsy clip fiducial marker will be placed in the region of the tumor to provide localization for radiotherapy delivery. Kilovoltage on-board-imaging (OBI) and/or cone beam CT (CBCT) will be used for localization as described in the section on target localization.

The patient will then undergo a research magnetic resonance (MR) for radiation treatment planning. The patient will be placed on the MR table with the breast pendant in a dedicated breast surface coil with arms raised overhead. Alternatively, the patient will be placed supine and specialized thoracic coils will be utilized in order to keep the breast in the same shape for the MR, CT, and radiation treatment to the extent possible. MR/CT compatible surface markers will be used to assist in this effort. T1-weighted imaging, T2-weighted imaging, inversion-recovery imaging, diffusion weighted imaging (DWI), and Dynamic contrast enhanced (DCE) MRI of the breast will be performed on the 1.5 Tesla GE Signa scanner in the Department of Radiation Oncology, equipped with a research key.

More specifically, T1 weighted MRI will be acquired with a 3D gradient-echo with spoiler (SPGR) sequence to achieve spatial resolution of sub-millimeter; T2 weighted MRI will be acquired with a 2D fast spin-echo (FSE) sequence; inversion recovery MRI will be acquired by a 2D axial short-T1 inversion-recovery (STIR) sequence; DCE-MRI will be acquired with a 3D SPGR sequence. Before DCE-MRI acquisition, a MedRad Power Injector will be used to administer weight appropriate dose of gadolinium at 2cc/second after a 30 second inject delay.

Axial T1, axial short-T1 inversion-recovery (STIR), and dynamic VIBRANT images will be required for the delineation of the enhancing tumor, the gross tumor volume (GTV). A planning CT scan will also be acquired in order to generate dose calculations.

Treatment Planning and Dose:

The MR images will be used to define the GTV. A 1.5 cm uniform expansion will be applied around the GTV to create the clinical target volume (CTV). MRI images will be fused to the CT images for further identification of normal structures and target volumes. The first 5mm of subcutaneous tissue and any chest wall (pectoralis muscle and deeper) if >1 cm from the GTV will be excluded from this volume. The first 5mm of tissue is in the photon "build-up" region and to include this area would skew the dose calculations. The chest wall is considered an anatomic boundary to tumor that is separate from the chest wall. An additional 0.5 cm margin to beam edge, will be used to generate the planning target volume (PTV) in order to account for set-up uncertainty. A PTV eval will be utilized for analysis of dose coverage. The PTV eval will include the same volume as the PTV with the exception of the first 5mm of skin. The CTV will be utilized for target dose-volume analysis.

The skin, ipsilateral and contralateral lung, ipsilateral and contralateral breast tissue, spinal cord and heart will be segmented as per institutional standard and analyzed for dose. The skin will be defined as a 3 mm layer from the external body surface. The ipsilateral and contralateral breast tissue will be segmented utilizing the guidelines from ongoing phase III NRG trials. In short, the breast tissue typically included in standard breast tangents minus the lungs and chest wall will be designated the breast volume with hand modification as needed by the principal investigator or designee.

The skin, spinal cord, and lungs will be auto-contoured in standard fashion. The heart should be contoured from the apex to the root of the great vessels. The thyroid and brachial plexus will also be contoured as appropriate depending on tumor location. The thyroid should be easily visible and contoured at the base of the neck. The brachial plexus should be visible on MRI and will be contoured with the assistance of radiology as indicated. Alternatively, the axillary vessels will be used as a surrogate for the brachial plexus²³.

A treatment plan utilizing arc therapy, or multiple conformal beams, or intensity-modulated therapy, or a combination of these techniques will then be designed. The beam arrangement can be organized in any fashion provided that the dose constraints listed below are met. The dose will be normalized to provide a desired coverage (95% to 98%) to the CTV. Subjects will receive a single fraction of 7 Gy.

Dose coverage (taken with some modifications to account for the single-dose preoperative delivery technique from the ongoing NRG phase III trial evaluating concurrent boost) will be considered appropriate as follows:

Target volume (CTV): prescribed dose covers >90% of the CTV without exceeding maximum dose of 110% of prescribed dose

Normal breast: <30% of the whole breast reference volume should receive 50% or more of the prescribed dose and <15% of the whole breast reference volume should receive the prescribed dose

Contralateral breast: the contralateral whole breast reference volume should receive <10% of the prescribed dose to any point

Lungs: Mean lung dose <3.6Gy, V5<10%

Heart: Mean should not exceed 50cGy, no point should receive greater than 4Gy, Dose to 1cc <2Gy

Thyroid: maximum point dose < 10% of the prescribed dose

Brachial plexus: no point in the brachial plexus should receive more than 10% (1Gy maximum) of the prescribed dose.

Skin dose: 1) Maximum dose will not exceed prescription dose. 2) Dose to 1cc: <6Gy (85% prescription)

Cord: maximum dose to 1 cc should be 1 Gy.

In addition, a low dose survey will be performed to ensure no unanticipated regions are receiving inappropriate dose.

Target Localization and Treatment Delivery:

Subjects will be taken to the treatment machine and positioned comfortably as they were at the time of CT simulation. Image-guidance will be used to localize the treatment volume, including on-board radiographic imaging and cone-beam CT. Cone-beam CT will always be completed except in cases where this is not technically feasible due to machine technical constraints. Positioning correction will be performed as necessary, verified and documented. Implanted marker may be considered as surrogates for effective target localization. The target localization procedure will be documented and adjustments will be made as appropriate. Treatment will be delivered to the target volume in one fraction. Each treatment plan will be checked for quality assurance in both calculation and dosimetry. All treatment will be recorded and verified through ARIA information system.

Post-operative Radiation:

Following pre-operative boost subjects will proceed to surgical resection. Systemic therapy will then be delivered as indicated and radiation will resume following systemic therapy in standard fashion. Alternatively, women will return following surgical resection and initiate conventional whole breast radiation +/- regional

nodal treatment as per standard procedures. Hypofractionated breast treatment will be considered an acceptable alternative to standard therapy (46-50Gy) when clinically appropriate.

Cosmesis, recurrence and late RT toxicities outcomes will be gathered and recorded separately for subjects deemed to require mastectomy based on unexpected findings at the time of surgical resection. It would not be accurate to compare the secondary endpoints of these subjects to those receiving breast conservation.

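### The bracketed 1 Gy in the brachial plexus constraint does not match the stated 10% limit, which is 0.7 Gy at the fixed 7 Gy prescription

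*Combined protocol and SAP*

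**What the plan says.** The dose is the same for everyone. Section 5.2 (Treatment Planning and Dose) states: "Subjects will receive a single fraction of 7 Gy". No other boost dose is prescribed.

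The same section lists the dose constraints, which are introduced as "taken with some modifications to account for the single-dose preoperative delivery technique" from another trial's criteria. The brachial plexus line reads: "no point in the brachial plexus should receive more than 10% (1Gy maximum) of the prescribed dose". The only other text on the plexus, earlier in section 5.2, concerns contouring. It makes contouring depend on where the tumor lies and gives no dose limit.

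Four neighbouring lines help in reading this one:

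- Skin, which pairs an absolute dose with a percentage: "Dose to 1cc: <6Gy (85% prescription".
- Thyroid, percentage only: "Thyroid: maximum point dose < 10% of the prescribed dose".
- Contralateral breast, percentage only: "the contralateral whole breast reference volume should receive <10% of the prescribed dose to any point".
- Spinal cord, absolute dose only: "Cord: maximum dose to 1 cc should be 1 Gy".

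The constraints are conditions on the plan: "The beam arrangement can be organized in any fashion provided that the dose constraints listed below are met". Section 4.2, exclusion criterion 7, excludes a subject whose planning constraints cannot be satisfied.

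**The concern.** The plexus line gives a percentage and an absolute dose for a single point-dose limit. With one fixed prescription the two should convert into each other, and they do not. The absolute figure is the looser of the two, and it carries the word maximum.

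What is at stake is the check on an individual plan. Someone entering an absolute dose objective may take the figure in gray straight from the bracket. A plan with a plexus maximum above 0.7 and up to 1.0 Gy would then be accepted although it exceeds 10% of the prescription. Because the constraints decide whether a plan may be used, and bear on eligibility through exclusion criterion 7, the line should carry one number.

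**Working it through.** **Inputs, all from section 5.2**

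- Prescribed dose: 7 Gy, single fraction, all subjects.
- Plexus limit: 10% of the prescribed dose, with 1 Gy in brackets.
- Skin limit to 1 cc: 6 Gy, with 85% in brackets.
- Thyroid and contralateral breast limits: 10%.
- Maximum dose allowed in the CTV: 110% of the prescribed dose.

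**Step 1. Try to reproduce the bracketed 1 Gy from the percentage.**
Limit in Gy = percentage × prescription = 0.10 × 7 Gy = 0.70 Gy. This is not 1 Gy.

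**Step 2. Convert the other way.**
1 Gy / 7 Gy = 14.3%. This is not 10%.

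**Step 3. Size of the gap.**
1.00 − 0.70 = 0.30 Gy, and 0.30 / 0.70 = 42.9%. The bracketed figure is about 43% above the stated limit.

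**Step 4. Try other bases.**

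- 10% of the CTV maximum: 0.10 × 1.10 × 7 Gy = 0.77 Gy. This does not give 1 Gy either.
- Prescription at which 10% equals 1 Gy: 1 / 0.10 = 10 Gy. This trial does not prescribe 10 Gy.

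No base at the 7 Gy prescription reconciles the two figures.

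**Step 5. Compare the other line that gives both units.**
Skin: 0.85 × 7 Gy = 5.95 Gy, written as 6 Gy. The gap is 0.05 Gy, and 0.05 / 5.95 = 0.8%. In reverse, 6 / 7 = 85.7%. The skin pair agrees closely at 7 Gy, so the plexus line stands out.

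**Step 6. Compare the single-unit lines.**
Thyroid and contralateral breast: 0.10 × 7 Gy = 0.70 Gy, the same as the percentage in the plexus line. The cord line uses 1 Gy as an absolute figure, the same as the plexus bracket, but for the dose to 1 cc, whereas the plexus limit applies to any point.

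**Step 7. Which plans are affected.**

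| Plexus maximum | Against 10% (0.7 Gy) | Against 1 Gy |
|---|---|---|
| up to 0.7 Gy | meets | meets |
| above 0.7 and up to 1.0 Gy | exceeds | meets |
| above 1.0 Gy | exceeds | exceeds |

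Only the middle row depends on which figure is applied.

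**The case against.** The strongest reply is that the line can be followed as written. The main clause caps every plexus point at 10%, and nothing in it allows that to be exceeded. If the bracket is a second, separate ceiling, both apply, the stricter one binds, and 1 Gy is merely redundant. On that view no conversion has failed, because the protocol never states that 10% equals 1 Gy. This reply largely stands. A reader might infer that the protocol leaves the governing limit open. The documents do not support that: the operative clause sets 10%, the thyroid and contralateral breast lines use the same percentage, and a planner who applies it makes no error. What remains is that a bracketed maximum looser than the limit beside it has no function at 7 Gy and invites misuse.

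A second reply is rounding. The skin figure fits rounding to a whole gray, and 0.7 rounded that way becomes 1. The skin line therefore cannot exclude rounding as the source of the 1 Gy. But the same list gives limits of 3.6 Gy and 50 cGy, so whole-gray rounding is not its general practice, and rounding a cap upward by 43% would still misstate it. The documents do not show where the 1 Gy came from.

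A third reply is that the consequence needs several conditions to hold together: the plexus is contoured, its maximum lies between 0.7 and 1.0 Gy, and the planner works from the bracket. For exclusion criterion 7 to be engaged, the plan must also be one that cannot be brought down to 0.7 Gy, although arcs, conformal beams and intensity modulation are all permitted. This stands, and it keeps the point minor. Section 5.2 also requires each plan to pass a quality assurance check of calculation and dosimetry, but that check does not say which figure to test against.

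**Conclusion.** The mismatch is certain: 0.7 Gy against 1.0 Gy, or 10% against 14.3% of the prescription. It rests only on the fixed 7 Gy dose and the wording of the line. Read literally, 10% governs and the bracketed figure never binds. The error is a wrong or redundant absolute figure in an operative constraint, and the practical risk is that a planner uses it.

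A reader might also infer a safety problem. The documents show none: nothing in them indicates that a plexus dose between 0.7 and 1.0 Gy causes harm. Nor do they allow a count of affected patients, since they give neither tumor locations nor plexus doses. That number is unknown.

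Severity is minor. The cosmesis endpoint, the sample size of 40, the 6-month review rule and the section 7 analyses are unaffected. Confidence is high for the arithmetic. It does not extend to how often plan approval or eligibility would turn on it, or to which figure the authors had in mind.

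**What to change.** Restate the brachial plexus line in section 5.2 as one limit: maximum point dose 10% of the prescription, with 0.7 Gy in brackets in place of 1 Gy. This keeps the main clause and agrees with the thyroid and contralateral breast limits. Apply that limit both in plan approval and in exclusion criterion 7.

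Only if the sponsor confirms that 1 Gy was the intended limit, make 1 Gy the stated cap and change the percentage to about 14%.

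The cost is a one-line protocol correction once the sponsor has confirmed the intended value. Sample size, schedule and analysis do not change.
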